4.5 Drop-out and treatment

4.5.1 Definition of drop-out: All patients who have completed the Informed Consent Form and screened to be enrolled in the trial have the right to withdraw at any time. Whenever and for whatever reason, subjects who fail to complete the observation period specified in the Protocol are considered as drop-out cases, including the following situations:

- The subject has serious adverse events and the clinician believes that he/she should withdraw from the clinical trial;
- The subject shows aggravated condition or has other symptoms affecting the trial observation during the trial, and the clinician believes that he/she should withdraw from the clinical trial;
- Important deviations occur in the implementation of clinical trial protocol, such as poor compliance, which would cause difficulty in evaluating the drug effect;
- The subject is unwilling to continue the clinical trial and asks to withdraw from the clinical trial, or loss of follow-up has occurred although no request to withdraw from the trial is proposed.

4.5.2 Treatment of drop-off cases: The investigators shall contact the drop-off subjects by means of visiting, making an appointment for follow-up, calling, letter and so on, to ask the reasons, record the last medication time and complete the evaluation items that can be completed. For the cases withdrawing from the trial due to allergy or other adverse reactions and ineffective treatment, the investigators shall take corresponding treatment measures according to the actual situation of the subjects. The investigators shall properly keep the relevant test data of the drop-off cases, not only for filing, but also for full analysis and statistics.

4.6 Relevant definitions in inclusion and exclusion criteria

4.6.1 Steroid-sensitive nephrotic syndrome (SSNS): Complete remission after 4 weeks of prednisone or prednisolone at standard dose [2mg/kg.d or 60mg/m². d].

- 4.6.2 Steroid-resistant nephrotic syndrome (SRNS):** Lack of complete remission at 4 weeks of therapy with daily prednisone or prednisolone at standard dose [2mg/kg.d or 60mg/m².d].
- 4.6.3 Steroid-dependent nephrotic syndrome (SDNS):** Two consecutive relapses during therapy with prednisone or prednisolone (either at full dose or during tapering) or within 15 days of prednisone or prednisolone discontinuation.
- 4.6.4 Frequently relapsing nephrotic syndrome (FRNS):** ≥ 2 relapses per 6 months within 6 months of disease onset or 24 relapses per 12 months in any subsequent 12-month period.
- 4.6.5 Secondary nephrotic syndrome:** It refers to the nephrotic syndrome with clear causes. Secondary nephrotic syndrome can be caused by autoimmune diseases (such as systemic lupus erythematosus), diabetes, infections (such as bacteria and hepatitis B virus), circulatory system diseases, drug poisoning, etc.

5. Test drugs and their allocation

5.1 Drug name and specifications

- (1) Tacrolimus capsules (trade name: Saifukai®, capsules, 1.0 mg/capsule, 0.5 mg/capsule);
Storage conditions: Keep away from sunlight, and store in a dry place below 25°C after sealing.
- (2) Mycophenolate mofetil dispersible tablets (trade name: Saikeping®, tablets, 250 mg/tablet);
Storage conditions: Store under 30°C and keep away from sunlight.
- (3) Storage conditions of prednisone tablets (tablets, 5 mg/tablet): Keep away from sunlight, and store at room temperature after sealing.

[Prednisone tablets can be replaced by other glucocorticoids during the test, but the dose shall have the same therapeutic effect, for example prednisone 5mg = prednisolone 5mg, prednisone 5mg = methylprednisolone 4mg, etc.]

5.2 Administration method, dose, route and course of treatment

5.2.1 Initial administration protocol

FK506 dose: 0.05-0.10 mg/kg/day, BID

Maintained concentration: In the induction period (the first six months after treatment) (visit 2, 3, 4, 5 and 6), the trough plasma concentration of tacrolimus is 5 - 10 ng/mL;

In the maintenance period, drug dose is gradually reduced when the patient's condition is stable:

In the last six months after administration (visit 7, 8, and 9), the trough concentration is <5 ng/mL

MMF dose: 20-30 mg/kg/day, BID

Plasma concentration (AUC) [Formula: $MPA-AUC = 7.75 + (6.49 * C_0) + (0.76 * C_{0.5}) + (2.43 * C_2)$]

Maintained concentration: In the induction period (the first six months after treatment) (visit 2, 3, 4, 5 and 6)

MPA-AUC=30 - 50 µg.h/mL

In the maintenance period, drug dose is gradually reduced when the patient's condition is stable:

In the last six months after administration (visit 7, 8, and 9), MPA-AUC ≤ 40 µg.h/mL

Prednisone dose: The initial dose is 1.0-1.5 mg/kg every other day or 0.5-0.75 mg/kg every day. The dose shall be reduced after 4 weeks by 0.25 mg/kg (qd alt) or 0.125 mg/kg (every day) every 2-4 weeks. If the condition is stable, continue to reduce to 5mg (body surface area > 1 m²) and 2.5mg (body surface area < 1 m²) qd alt. Maintain at such doses until this research is completed.

5.2.2 Treatment of relapses

If the disease is complicated with infection in the relapse for the pediatric patients, anti-infection treatment can be given first. After infection control, if the disease still shows relapse, the prednisone dose shall be restored to 1.0-1.5 mg/kg per day, with a maximum dose ≤ 60mg; If there is no infection at the time of relapse in the pediatric patients, the prednisone dose should be restored to 1.0-1.5 mg/kg per day directly, with a maximum dose ≤ 60mg. 5-7 days after the urine protein turns into negative results, the prednisone dose is reduced by 1.0-1.5 mg/kg every other day or 0.5-0.75mg/kg per day × 4 weeks. Then the dose is reduced as per the above steroid reduction method, while the dose of MMF or FK506 remains unchanged.

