5.2.3 Dose adjustment of tacrolimus (FK506)

5.2.3.1 Adjust the dose according to the trough plasma concentration of tacrolimus. If the trough plasma concentration cannot meet the target concentration, it can be increased by adding Wuzhi capsules, ketoconazole, Hexin Shuang or cimetidine. If the trough plasma concentration of tacrolimus is >10 ng/mL, the dose of tacrolimus shall be reduced, and the trough concentration shall be rechecked after one week to adjust the target concentration. After treatment, the increase of SCr ≥ 30% of the basic value and eGFR < 60mL/min.1.73m² (excluding non-drug factors) shall prompt tacrolimus dose reduction by 50%. If the concentration still fails to reach the target after tacrolimus dose adjustment for one month, the subject shall withdraw from the trial.

5.2.3.2 If the trough plasma concentration of tacrolimus in visit 7 is ≥ 5 ng/mL, the dose of tacrolimus needs to be reduced by 20%-30%, and the trough concentration shall be rechecked in visit 8. If the trough concentration of tacrolimus is still ≥ 5 ng/mL in visit 8,

it is necessary to continue to reduce the dose of tacrolimus by 20%-30%, and recheck this concentration in visit 9.

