5.2.4 Dose adjustment of mycophenolate mofetil (MMF)

5.2.4.1 Adjust the dose according to the plasma concentration of mycophenolic acid. If MPA-AUC fails to meet the target, increase the oral dose of mycophenolate mofetil, but the maximum dose shall not exceed 1.0g each time, BID. Recheck MPA-AUC after 1 week and adjust the drug administration to meet the target concentration. If the patient has blood neutrophils less than 1300 per μL or total leukocytes less than 3000 per μL , diarrhea or severe infection, the dose of mycophenolate mofetil needs to be reduced by 25%. If the side effect persists, it shall be adjusted to half of the original dose. If the case of mycophenolate mofetil dose adjustment, the plasma concentration shall be measured according to the judgment of the investigators. If the concentration still fails to reach the target after mycophenolate mofetil dose adjustment for one month, the subject shall withdraw from the trial.

5.2.4.2 If MPA-AUC is ≥ 40 ng/mL in visit 6, the dose of mycophenolate mofetil needs to be reduced by 20%-30%. After that, retest is no longer required.

5.3 concomitant medication

- Statins are allowed for use during this research, which can be increased or decreased according to the blood lipid status.
- Various anticoagulant drugs are allowed for use during this research.
- Immunosuppressants other than the test drug are prohibited for use.
- Plasma exchange and biological agents are prohibited for treatment.
- IVIG can be used during this research, but the reason needs to be recorded.
- When hypertension occurs during treatment, angiotensin converting enzyme inhibitor (ACEi) or angiotensin II receptor blocker (ARB) cannot be used, but dihydropyridine calcium antagonists, β -receptor blocker, diuretic and/or α -receptor blocker can be used for control, with a target blood pressure of: $<120/80$ mmHg.
- Liver protection drugs are allowed for use during this research.
- If blood glucose rises during treatment, the blood glucose shall be actively controlled with hypoglycemic drugs.
- Various Chinese herbal medicines are prohibited for the treatment of kidney diseases during this research.
- The investigators shall ask the subjects to bring all the drugs they are taking at the time of follow-up, so as to check the concomitant medication for the subjects. For the other drugs or treatments that must be continued for the complicated diseases, the drug name (or

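### A child tapering steroids after a relapse can be told both to keep the MMF or tacrolimus dose unchanged and to cut it by 20-30%

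*Protocol*

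**What the plan says.** Four pieces of current text govern the study-drug dose of a child who has relapsed. The SAP repeats all four under the same section numbers.

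- **Protocol 5.2.2 (relapse).** Prednisone is raised, then stepped down once the urine clears, "while the dose of MMF or FK506 remains unchanged". No end to this hold is stated.
- **Protocol 5.2.1 (maintenance).** For each drug: "In the maintenance period, drug dose is gradually reduced when the" condition is stable. Stable is not defined.
- **Protocol 5.2.3.2 (tacrolimus).** "If the trough plasma concentration of tacrolimus in visit 7 is ≥ 5 ng/mL", then "the dose of tacrolimus needs to be reduced by 20%-30%, and the trough concentration shall be rechecked in visit 8". A second cut of the same size follows if the Visit 8 trough is still at least 5 ng/mL.
- **Protocol 5.2.4.2 (MMF).** If the Visit 6 MPA-AUC is at or above 40, "the dose of mycophenolate mofetil needs to be reduced by 20%-30%. After that, retest is no longer required". The threshold is printed in ng/mL, whereas 5.2.1 gives the AUC target in µg.h/mL.

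The flow chart puts Visit 6 at Day 168, Visit 7 at Day 224 and Visit 8 at Day 280. Relapse is not among the mandatory withdrawal criteria in Protocol 4.4, so a relapsed child can still be on study drug at these visits.

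**The concern.** The hold in 5.2.2 and the cuts in 5.2.3.2 and 5.2.4.2 can apply to the same child on the same day, and neither text says which gives way. The plan's own targets make the overlap likely. Section 5.2.1 sets the tacrolimus trough at 5-10 ng/mL through Visit 6, so a child who is on target and held unchanged would be expected to read at least 5 at Visit 7, which triggers the cut. For MMF, the trigger of 40 takes in the upper half of the 30-50 target that 5.2.1 applies at Visit 6 itself.

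The trial is open-label, so each site resolves the conflict knowing the arm. Whether immunosuppression is lowered soon after a relapse can affect later relapses and the steroid they require. Relapse frequency and cumulative steroid dose are both secondary outcomes (Protocol 7.2.2). The steroid effect would fall mainly on the whole-study total, because the checks start at Day 168. Safety is also exposed. Site-to-site variation in an unrecorded dosing rule could not be separated from the drug effect on these outcomes.

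**Working it through.** **1. The rules side by side, for a child in remission but still on the post-relapse taper, at or above the threshold**

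| Text | Instruction |
|---|---|
| 5.2.2 | Hold the dose |
| 5.2.3.2 or 5.2.4.2 | Cut by 20-30% |
| 5.2.1, if such a child is not stable | No maintenance reduction yet |
| 5.2.1, if such a child is stable | Reduce |

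Section 5.2.1 does not break the tie, because its answer depends on an undefined word.

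**2. Can the taper still be running at the check?** I read the 5.2.2 step as going down to 1.0-1.5 mg/kg every other day for 4 weeks, starting about 1 week after the urine clears. Section 5.2.1 then removes 0.25 mg/kg every 2-4 weeks. Assume a 20 kg child and a 2.5 mg floor (0.125 mg/kg).

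- Shortest: from 1.0 mg/kg with 2-week steps, doses of 0.75, 0.5, 0.25 and 0.125 start at weeks 4, 6, 8 and 10. Adding 1 week gives about 11 weeks.
- Longest: from 1.5 mg/kg with 4-week steps, doses of 1.25, 1.0, 0.75, 0.5, 0.25 and 0.125 start at weeks 4, 8, 12, 16, 20 and 24. Adding 1 week gives about 25 weeks.

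The checks fall at week 24 (168/7) for MMF and week 32 (224/7) for tacrolimus. A taper of 11 to 25 weeks can easily span either.

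**3. How many children could be involved?** Inputs: 1-year relapse-free survival of 0.56 (MMF) and 0.70 (FK506), and 135 per arm (Protocol 3.3.2).

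Check against the plan's own figure: under constant hazards, HR = ln(0.70)/ln(0.56) = 0.6151, as in Appendix 4. With uniform accrual over 2 of 3 years and 114 + 115 children, this gives 133.7 expected events and power 0.802, against the stated 133.8 and 0.8009. The point does not rest on the sample size; the check only shows that the rates are used as the plan uses them.

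Proportion relapsed by day t = 1 − S^(t/365), where S is the 1-year relapse-free survival; no loss assumed:

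| Arm and check | Proportion relapsed | × 135 | Across the ±7-day window |
|---|---|---|---|
| MMF, Visit 6, Day 168 | 1 − 0.56^(168/365) = 0.234 | 31.6 | 30.5 to 32.8 |
| FK506, Visit 7, Day 224 | 1 − 0.70^(224/365) = 0.197 | 26.5 | 25.8 to 27.3 |
| FK506, Visit 8, Day 280 | 1 − 0.70^(280/365) = 0.239 | 32.3 | not computed |

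These are ceilings under the stated assumptions, not counts of conflicts. A child must also be at or above the threshold and still within the hold. The documents give neither share, so the fraction in actual conflict may lie anywhere from 0 to 100% of these figures. If relapses came earlier than a constant hazard implies, the ceiling would rise, but not beyond all first-year relapses: 0.44 × 135 = 59 for MMF and 0.30 × 135 = 41 for FK506 (rounded).

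**The case against.** **The 5.2.2 clause may be narrow.** It sits inside a sentence on steroid reduction and may mean only that a relapse is not in itself a reason to change the study drug. A freeze against every other rule would also block the reductions for a trough above 10 ng/mL, for renal change and for leukopenia, which is implausible. This stands as a possible reading, and it leads to the cut.

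**Section 5.2.1 may supply the exception.** The cut rules serve the maintenance targets, which are introduced with the stability condition. This too is possible, but it leads to the hold. Two reasonable ways of removing the conflict thus give opposite instructions, which is the problem.

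**The hold may end with the taper.** The clause is tied to the taper, which has a defined maintenance dose, so an end can be inferred. That stands, but it is not written, and section 5.2.2 would then still overlap the checks.

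**Some relapsed children may have left.** The note to SAP Table 1 counts subjects who withdrew because of the endpoint event as completers. This may reduce the numbers, though 5.2.2 plainly provides for continued treatment.

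**A stronger reading that does not hold.** Because the step-down check is at Visit 6 for MMF and Visit 7 for tacrolimus, 56 days apart, a reader might infer that tacrolimus is kept at induction exposure for longer and that the primary comparison is tilted. The documents do not support this. Section 5.2.1 allows tacrolimus reduction from the start of maintenance and expects a trough below 5 ng/mL by Visit 7. Both drugs are measured from Visit 2, and tacrolimus also at Visit 6. MPA is scheduled only at Visits 2 and 6. The different timing is drug-specific monitoring within the regimens being compared, not a contradiction.

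**Conclusion.** The dosing text conflicts, and the conflict is in the current protocol and in the SAP. It concerns a child who has relapsed, is still on the post-relapse taper, and is at or above the concentration threshold at Visit 6 (MMF) or at Visit 7 or 8 (tacrolimus). Other children are not affected.

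A reader might infer that this biases the primary endpoint. It cannot alter an affected child's own primary event: SAP 8.1.3 times relapse from randomisation, and the conflict arises only once a relapse has occurred. For the same reason it leaves time to first relapse unchanged. What it can affect is relapse frequency, cumulative steroid dose and safety, in a direction the documents do not determine.

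The ceiling is about 32 of 135 MMF children (23%) by Day 168 and 27 of 135 tacrolimus children (20%) by Day 224. It assumes the plan's 1-year rates, constant hazard and no loss. The number in actual conflict cannot be calculated from the documents. This is a moderate clarification of conflicting dosing text, not a flaw in the primary analysis.

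**What to change.** Reconcile Protocol 5.2.1, 5.2.2, 5.2.3.2 and 5.2.4.2, and SAP 5.2.1-5.2.4 with them, so that:

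1. one instruction applies to a child who is in a relapse, or tapering after one, when the Visit 6, 7 or 8 level is read;
2. the end of the hold in 5.2.2 is stated;
3. stable in 5.2.1 is defined, and the cut rules say whether they depend on it;
4. the CRF records which rule was applied to each such child.

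The unit printed for the MPA-AUC threshold in 5.2.4.2 should be reconciled with 5.2.1 in the same edit. Which dosing rule applies is a clinical decision for the sponsor, and none is proposed here.

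The cost is a short clarification in both documents, a notice to sites and one CRF field. Sample size and the primary analysis do not change.

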5.2.3 Dose adjustment of tacrolimus (FK506)

5.2.3.1 Adjust the dose according to the trough plasma concentration of tacrolimus. If the trough plasma concentration cannot meet the target concentration, it can be increased by adding Wuzhi capsules, ketoconazole, Hexin Shuang or cimetidine. If the trough plasma concentration of tacrolimus is >10 ng/mL, the dose of tacrolimus shall be reduced, and the trough concentration shall be rechecked after one week to adjust the target concentration. After treatment, the increase of SCr ≥ 30% of the basic value and eGFR < 60mL/min.1.73m² (excluding non-drug factors) shall prompt tacrolimus dose reduction by 50%. If the concentration still fails to reach the target after tacrolimus dose adjustment for one month, the subject shall withdraw from the trial.

5.2.3.2 If the trough plasma concentration of tacrolimus in visit 7 is ≥ 5 ng/mL, the dose of tacrolimus needs to be reduced by 20%-30%, and the trough concentration shall be rechecked in visit 8. If the trough concentration of tacrolimus is still ≥ 5 ng/mL in visit 8,

it is necessary to continue to reduce the dose of tacrolimus by 20%-30%, and recheck this concentration in visit 9.

5.2.4 Dose adjustment of mycophenolate mofetil (MMF)

5.2.4.1 Adjust the dose according to the plasma concentration of mycophenolic acid. If MPA-AUC fails to meet the target, increase the oral dose of mycophenolate mofetil, but the maximum dose shall not exceed 1.0g each time, BID. Recheck MPA-AUC after 1 week and adjust the drug administration to meet the target concentration. If the patient has blood neutrophils less than 1300 per μL or total leukocytes less than 3000 per μL , diarrhea or severe infection, the dose of mycophenolate mofetil needs to be reduced by 25%. If the side effect persists, it shall be adjusted to half of the original dose. If the case of mycophenolate mofetil dose adjustment, the plasma concentration shall be measured according to the judgment of the investigators. If the concentration still fails to reach the target after mycophenolate mofetil dose adjustment for one month, the subject shall withdraw from the trial.

5.2.4.2 If MPA-AUC is ≥ 40 ng/mL in visit 6, the dose of mycophenolate mofetil needs to be reduced by 20%-30%. After that, retest is no longer required.

5.3 concomitant medication

- Statins are allowed for use during this research, which can be increased or decreased according to the blood lipid status.
- Various anticoagulant drugs are allowed for use during this research.
- Immunosuppressants other than the test drug are prohibited for use.
- Plasma exchange and biological agents are prohibited for treatment.
- IVIG can be used during this research, but the reason needs to be recorded.
- When hypertension occurs during treatment, angiotensin converting enzyme inhibitor (ACEi) or angiotensin II receptor blocker (ARB) cannot be used, but dihydropyridine calcium antagonists, β -receptor blocker, diuretic and/or α -receptor blocker can be used for control, with a target blood pressure of: $<120/80$ mmHg.
- Liver protection drugs are allowed for use during this research.
- If blood glucose rises during treatment, the blood glucose shall be actively controlled with hypoglycemic drugs.
- Various Chinese herbal medicines are prohibited for the treatment of kidney diseases during this research.
- The investigators shall ask the subjects to bring all the drugs they are taking at the time of follow-up, so as to check the concomitant medication for the subjects. For the other drugs or treatments that must be continued for the complicated diseases, the drug name (or

other treatment name), dosage, times of use and time must be recorded on the Clinical Study Report for analysis and reporting during summary.

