5. \$ items are applicable to the pediatric patients with combined use of other immunosuppressants before enrollment; © items are optional, depending on the judgment and decision of the investigators;
6. This research accepts the examination data from our hospital within 2 weeks before the screening period, and no repeated test is needed.

1. Background

Primary nephrotic syndrome, the most common glomerular disease in children, accounts for about 90% of the total nephrotic syndrome cases in pediatric patients^[1]. It is reported that the annual incidence rate of pediatric nephrotic syndrome is about 2-4/100000, and the prevalence rate is about 16/100000^[2, 3]. The statistics of hospitalized children in some provincial and municipal hospitals in China show that primary nephrotic syndrome accounts for about 20% of hospitalized children with urinary system diseases^[4]. Renal biopsy shows minimal lesions in more than 80% of patients. This disease can occur at any age, but it mostly occurs at the age of 2-6. It is more common in boys, with a male/female ratio of about 3:2. Since the 1950s, glucocorticoids have been recognized as the first-line treatment. About 80%-90% of pediatric patients with primary nephrotic syndrome can achieve complete remission after initial steroid treatment, but 76%-93% of the pediatric patients have relapses, of which 45%-50% show frequent relapses (FR) or steroid dependence (SD)^[5]. The relapses of proteinuria, especially frequently relapsing/steroid-dependent nephrotic syndrome, have always been a very difficult and urgent problem for clinicians. Some pediatric patients may have steroid resistance after repeated relapses and eventually develop into chronic dysfunction. The long-term or repeated use of steroids at high doses will lead to side effects such as obesity, growth inhibition, hypertension, diabetes, glaucoma, cataract, osteoporosis and serious infection. Its combined use with traditional immunosuppressants such as cyclophosphamide and cyclosporine A (CSA) will bring some serious irreversible side effects. Therefore, it is particularly important to explore new immunosuppressants and their application schemes.

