4.1 Inclusion criteria

Only those who meet all the conditions listed in this column can be considered for inclusion in this research:

- (1) Steroid-sensitive nephrotic syndrome with frequent relapse (FRNS) or steroid dependence (SDNS);
- (2) Age: 2-18 years old;
- (3) Normal renal function: $eGFR \geq 90 \text{ mL/min/1.73m}^2$;
- (4) At the time of enrollment, urinary protein $< 1+$ or urinary protein/creatinine $< 0.2 \text{ g/g}$ ($< 20 \text{ mg/mmol}$) in the morning for 3 consecutive days or more;
- (5) No use of tacrolimus, mycophenolate mofetil, cyclosporine A, rituximab or cyclophosphamide within 2 years before enrollment;

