7.2 Efficacy evaluation

7.2.1 Primary observation outcomes: 1-year relapse-free survival

7.2.2 Secondary observation outcomes:

- (1) Frequency of relapses; the time of the first relapse after enrollment; relapse-free **survival** in the first six months after enrollment;
- (2) Renal function: Serum creatinine and glomerular filtration rate (eGFR, see Appendix 1 for the calculation method)
- (3) Cumulative steroid dosage: The total amount of steroids taken during this research and the total amount of steroids in the first half of the year
- (4) Others: Blood pressure (see Appendix 2 for details), height, weight, blood lipid, hemoglobin, blood albumin, urinary protein/creatinine (morning urine), etc.
- (5) Adverse reaction
- (6) 24hr urinary protein quantification (applicable to subjects > 3 years old)

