Like other potent immunosuppressants, tacrolimus administration shows an increased risk of infection (viruses, bacteria, fungi and protozoa). Existing infections may be aggravated, and the systemic and local infections may occur. Patients treated with immunosuppressants, including tacrolimus, have been reported to have BK virus-related nephropathy and JC virus-related progressive multifocal leukoencephalopathy (PML).

Injury, intoxication and operation complications

Benign, malignant and unclear tumors (including cysts and polyps). Patients treated with immunosuppressants have an increased risk of malignant tumors. Benign and malignant tumors,

including EBV-related lymphoid hyperplasia and skin malignancies, have been reported to have possible association with the tacrolimus treatment.

Vascular abnormalities

Very common: Hypertension; Common: Bleeding, thrombus and local ischemia, peripheral vascular abnormalities, and hypotension; Unusual: infarction, limb deep vein thrombosis, and shock.

General abnormalities and administration site symptoms

Common: Weakness, fever, edema, pain and discomfort, elevated blood alkaline phosphatase, weight gain, and body temperature sensation disorder; Unusual: Multiple-organ failure, influenza like symptoms, temperature intolerance, chest compression, tension, paresthesia, elevated blood lactate dehydrogenase and weight loss; Rare: Thirst, fall, reduced activity, and ulcer; Very rare: Increased adipose tissue; Unknown: Death or sudden cardiac death, and abnormal gait.

Immune system abnormalities and hepatobiliary abnormalities

Allergic and anaphylactic reactions are observed in patients treated with tacrolimus.

Common: Abnormal liver function, cholestasis and jaundice, hepatocyte injury, hepatitis and cholangitis; Rare: Hepatic artery thrombosis, and venous occlusive liver disease; Very rare: Liver failure, and biliary stricture;

Reproductive system and breast abnormalities

Unusual: Dysmenorrhea and uterine bleeding; Unknown: Benign prostatic hyperplasia, and mental disorders; Very common: Insomnia; Common: Anxiety, confusion and disorientation, despondency, depression, emotional instability and disorder, nightmares, hallucinations and mental disorders; Unusual: Mental abnormality; Unknown: Aggressive behavior, and agitation.

8.1.2 Concerned adverse reactions of test drug MMF:

Infection

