12.1 Ethical review

The clinical trial protocol shall be submitted to the Ethics Committee for approval before implementation. If this Protocol is to be revised during the clinical trial implementation, it shall be submitted to the Ethics Committee for approval again before implementation. If important but new information concerning the test drugs is found, the Informed Consent Form must be revised in writing and submitted to the Ethics Committee for approval before signing by the subjects again.

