Appendix 2 Blood pressure reference values for children

Boy

Age		Diastolic blood pressure, mmHg												
		Systolic blood pressure, mmHg							Height percentile					
		Height percentile												
5th	10th	25th	50th	75th	90th	95th	5th	10th	25th	50th	75th	90th	95th	
	98	99	101	103	104	106	106	54	54	55	56	57	58	58
2	101	102	104	106	108	109	110	59	59	60	61	62	63	63
3	104	105	107	109	110	112	113	63	63	64	65	66	67	67
4	106	107	109	110	112	114	115	66	67	68	69	70	71	71
5	108	109	110	112	114	115	116	69	70	71	72	73	74	74
6	109	110	112	114	115	117	117	72	72	73	74	75	76	76
7	110	111	113	115	117	118	119	74	74	75	76	77	78	78
8	111	112	114	116	118	119	120	75	76	77	78	79	79	80
9	113	114	116	118	119	121	121	76	77	78	79	80	81	81
10	115	116	117	119	121	122	123	77	78	79	80	81	81	82
11	117	118	119	121	123	124	125	78	78	79	80	81	82	82
12	119	120	122	123	125	127	127	78	79	80	81	82	82	83
13	121	122	124	126	128	129	130	79	79	80	81	82	83	83
14	124	125	127	128	130	132	133	80	80	81	82	83	84	84
15	126	127	129	131	133	134	135	81	81	82	83	84	85	85
16	129	130	132	134	135	137	137	82	83	83	84	85	86	87
17	131	132	134	136	138	139	140	84	85	86	87	87	88	89

Girl

Age	Systolic blood pressure, mmHg							Diastolic blood pressure, mmHg						
	Height percentile							Height percentile						
	5th	10th	25th	50th	75th	90th	95th	5th	10th	25th	50th	75th	90th	95th
1	100	101	102	104	105	106	107	56	57	57	58	59	59	60
2	102	103	104	105	107	108	109	61	62	62	63	64	65	65
3	104	104	105	107	108	109	110	65	66	66	67	68	68	69
4	105	106	107	108	110	111	112	68	68	69	70	71	71	72
5	107	107	108	110	111	112	113	70	71	71	72	73	73	74
6	108	109	110	111	113	114	115	72	72	73	74	74	75	76
7	110	111	112	113	115	116	116	73	74	74	75	76	76	77
8	112	112	114	115	116	118	118	75	75	75	76	77	78	78
9	114	114	115	117	120	121	122	77	77	77	78	79	80	80
10	116	116	117	119	120	121	122	77	77	77	78	79	80	80
11	118	118	119	121	122	123	124	78	78	78	79	80	81	81
12	119	120	121	123	124	125	126	79	79	79	80	81	82	82
13	121	122	123	124	126	127	128	80	80	80	81	82	83	83
14	123	123	125	126	127	129	129	81	81	81	82	83	84	84
15	124	125	126	127	129	130	131	82	82	82	83	84	85	85
16	125	126	127	129	130	131	132	82	82	83	84	85	85	86
17	125	126	127	129	130	131	132	82	83	83	84	85	85	86

The blood pressure at 95th percentile standard¹⁴

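### The single blood pressure target of <120/80 mmHg lies above the protocol's own 95th percentile for every child aged 2 to 7

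*Protocol*

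**What the plan says.** Protocol 5.3 opens its rule with "When hypertension occurs during treatment, angiotensin converting enzyme inhibitor (ACEi) or angiotensin II receptor blocker (ARB) cannot be used". It then names four permitted classes that "can be used for control, with a target blood pressure of" <120/80 mmHg. SAP 5.3 carries the same rule. Neither section adjusts the figure for age, sex or height, and neither says what reading counts as hypertension.

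The inclusion criterion in Protocol 4.1 is "Age: 2-18 years old".

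Protocol Appendix 2 is a table by age, sex and height percentile, labelled "The blood pressure at 95th percentile standard". The protocol refers to it for the secondary outcome in 7.2.2: "Blood pressure (see Appendix 2 for details), height, weight, blood lipid". SAP 6.2.2 makes the same reference. Nothing in either document connects Appendix 2 to the treatment target in 5.3.

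**The concern.** A fixed threshold of 120/80 means very different things to a 3-year-old and a 16-year-old. The protocol recognises this for its outcome, where it uses a reference indexed by age, sex and height, but not for its treatment rule. If the fixed target lies above the reference in the youngest children, a site that follows 5.3 to the letter could leave a treated child above the trial's own 95th percentile.

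The situation is foreseeable. For tacrolimus, Protocol 8.1.1 lists under vascular abnormalities "Very common: Hypertension; Common: Bleeding, thrombus and local ischemia". The Background section names hypertension among the consequences of long-term or repeated high-dose steroids: "side effects such as obesity, growth inhibition, hypertension, diabetes". Both arms take steroids throughout (Protocol 6).

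**Working it through.** **Inputs.** The target of <120/80 mmHg is from Protocol 5.3 and SAP 5.3. The 95th percentiles are from Protocol Appendix 2: seven height columns, with systolic and diastolic values paired by column, for each age and sex. The boys' first row has lost its age label in the text supplied. The labelled boys' rows run from 2 to 17 and the girls' table starts at 1, so the unlabelled row is age 1 and is not used.

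**Step 1: count cells.** A cell is one age and one height column. It counts as below target if its systolic value is <120 and its diastolic value is <80.

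| Ages | Cells per sex | Boys, both below | Girls, both below |
|---|---|---|---|
| 2–7 | 6 × 7 = 42 | 42 | 42 |
| 8–13 | 6 × 7 = 42 | 6+4+3+3+1+0 = 17 | 7+4+4+3+1+0 = 19 |
| 14–17 | 4 × 7 = 28 | 0 | 0 |
| 2–17 | 112 | 59 | 61 |

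At ages 8–13, at least one of the two values is below target in 22 of 42 boys' cells and 24 of 42 girls' cells. At ages 14–17 the target is at least as strict as the percentile.

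**Step 2: size of the gap at median height.** Gap = 120 − systolic percentile / 80 − diastolic percentile, in mmHg.

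| Age | Boys' 95th | Gap | Girls' 95th | Gap |
|---|---|---|---|---|
| 2 | 106/61 | 14/19 | 105/63 | 15/17 |
| 3 | 109/65 | 11/15 | 107/67 | 13/13 |
| 4 | 110/69 | 10/11 | 108/70 | 12/10 |
| 5 | 112/72 | 8/8 | 110/72 | 10/8 |
| 6 | 114/74 | 6/6 | 111/74 | 9/6 |
| 7 | 115/76 | 5/4 | 113/75 | 7/5 |

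Over all height columns at ages 2–7, the gap runs from 1 to 19 systolic and 2 to 21 diastolic in boys, and from 4 to 18 and 3 to 19 in girls.

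**Step 3: whole-number readings.** The highest on-target reading is 119/79. Among the 84 cells at ages 2–7, 119 exceeds the systolic percentile in 83. The exception is the 7-year-old boy in the tallest column, whose percentile is 119. The value 79 exceeds the diastolic percentile in all 84, the highest being 78. So in every one of these cells an on-target reading can exceed at least one percentile.

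**Step 4: an example.** A 4-year-old boy of median height at 115/75 is above his 95th percentile of 110/69 and below 120/80. If a site diagnoses hypertension from Appendix 2, that one reading is both hypertensive and on target.

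**The case against.** The other side has four points.

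- **The figure is a ceiling.** An investigator may aim lower. That is true, but 5.3 does not ask for it and gives no other number.
- **Appendix 2 serves the outcome.** The documents never make it a diagnostic or treatment threshold, nor say that treated children should be brought below the 95th percentile. This stands as far as it goes: the both-hypertensive-and-on-target reading depends on a site using Appendix 2 for diagnosis. The comparison of target with percentile does not. Appendix 2 is also the only blood pressure reference in the text supplied.
- **Other sections protect the child.** Protocol 12.4 makes investigators responsible for medical care. Protocol 8.3 requires vital signs that worsen from baseline and meet the adverse event criteria to be reported. Both soften the concern, but neither supplies a number suited to a young child.
- **It may be too late.** SAP 4.1 describes enrolment as complete, and Protocol 15.3 plans the end of observation for July 2022. Whether any child would still be on treatment after an amendment cannot be told from the documents. This limits the benefit but not the finding.

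**Conclusion.** The concern holds. The written target is above the protocol's own 95th percentile in every cell at ages 2 to 7, and in some cells up to age 12. For girls the complete overlap extends to age 8. The gap is widest in the youngest children.

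The cell counts describe the table, not patients. The share of enrolled children in this age band is not given, so the number affected is unknown. No test, estimand, primary endpoint or sample size depends on this, and the documents do not show that the blood pressure comparisons are biased. It is an optional, low-priority improvement to the care instructions. It rests on Appendix 2 as supplied; the age 2–7 rows used here are unambiguous.

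**What to change.** In Protocol 5.3, replace the target with: below the Protocol Appendix 2 95th percentile for age, sex and height, and in all cases <120/80 mmHg (<120/80 alone at age 18, which the table does not cover). State in the same place which reference defines hypertension. Carry the wording into SAP 5.3 for consistency; it changes no analysis. Keeping <120/80 as a cap means that no child's target is loosened.

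Before sites rely on the table, check the girls' age-9 row. In the text supplied it shares 10 of its 14 values with the age-10 row, which may be a fault in reading the PDF.

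**Cost.** One line in each document and no new measurement, because height and vital signs are already taken at every visit. Sites would have to look up a height percentile, and the protocol supplies no height chart; SAP Table 34 draws height percentile from an external file. Some young children would be treated to a lower pressure. Under Protocol 12.1, if the protocol is revised during the trial, "it shall be submitted to the Ethics Committee for approval again before implementation", so only children still on treatment after approval would benefit.
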